Appendix 2: Schedule of Events (Every 3 Week Administration)

| Timing of Visit | Rollover Entry/ Cycle 1 Day 1 ¹ | Day 1 (\pm 3 days) of Subsequent Cycles ² | Rollover End of Study |
|---|---|---|------------------------------------|
| | | Every 3 Weeks | 28 \pm 7 days after last dose |
| Informed Consent | X | | |
| Eligibility Criteria | X | | |
| Physical Examination ³ | X | X | X |
| Weight (kg) | X | X | X |
| Vital Signs ⁴ | X | X | X |
| Pregnancy Test ⁵ | X | X | |
| Hematology | X | X | X |
| Chemistry | X | X | X |
| Other Laboratory Assessments per Standard of Care | X | X | X |
| Blood Samples for Pharmacodynamic Biomarkers | X | X ⁶ | X |
| Study Treatment Administration ⁷ | X | X | |
| Disease Imaging (e.g., CT scan) | | X ⁸ | X ⁸ |
| Concomitant Medications | X | X | X |
| Adverse Events | X | X | X |

Abbreviations: CT = computed tomography; RECIST = Response Evaluation Criteria in Solid Tumors

Footnotes:

¹ Enrollment into the rollover study should occur upon exit from the parent study to avoid any interruptions in study treatment administration.² All assessments should be performed prior to vopratelimab dosing, unless otherwise noted.³ Targeted physical examination is required on study administration days and at the End-of-study visit;⁴ Vital signs to include temperature, heart rate, respiratory rate, blood pressure, and oxygen saturation. Vital signs should be taken prior to and at the end of vopratelimab infusion.⁵ Negative serum or urine pregnancy test for women of childbearing potential prior to administration of vopratelimab on Day 1 of each treatment cycle.⁶ Blood sampling for exploratory analyses of pharmacodynamic biomarkers should be collected approximately every 3 months (\pm 4 weeks) at the time of a scheduled clinic visit. Sample collection may be discontinued at any time per the sponsor's discretion. Please refer to the Study Laboratory Manual for more details.⁷ Study treatment (vopratelimab \pm partner drug) should be administered on the same dose and schedule as a subject was receiving at the time of discontinuation from the parent study. Any changes to the dose and schedule of vopratelimab must be in accordance with a dose and schedule previously shown to be safe and well tolerated and must be discussed with the medical monitor. Any changes to the dose and schedule of nivolumab or ipilimumab must be discussed with the medical monitor.⁸ Disease imaging will be performed in accordance with institutional standard of care guidelines, but at least every 6 months (\pm 3 weeks). Response will be determined by RECIST (Version 1.1).

Appendix 3: Web Links

CTCAE

The link to the Common Terminology Criteria for Adverse Events (CTCAE) Version 5.0 is:

https://ctep.cancer.gov/protocolDevelopment/electronic_applications/docs/CTCAE_v5_Quick_Reference_8.5x11.pdf

FDA Guidance for Investigators

The below links are to the Guidance Documents for Investigators Responsibilities and Safety Reporting Requirements for INDs:

<http://www.fda.gov/downloads/Drugs/GuidanceComplianceRegulatoryInformation/Guidances/UCM227351.pdf>

<http://www.fda.gov/downloads/Drugs/.../Guidances/UCM187772.pdf>

Jounce Therapeutics, Inc.

Protocol JTX-2011-R01
Version 2.0, 03 August 2021

Appendix 4: RECIST

See Laboratory Manual for more information

http://ctep.cancer.gov/protocolDevelopment/docs/recist_guideline.pdf

{Eisenhauer, 2009}

## ABBREVIATIONS

AE	Adverse event
CR	Complete Response
CRF	Case Report Form
DOOR	Duration of Response
ECGs	Electrocardiograms
ECOG	Eastern Cooperative Oncology Group
eCRF	Electronic Case Report Form
EDC	Electronic Data Capture
irAEs	Immune related adverse events
IRRs	Infusion related reactions
MedDRA	Medical Dictionary for Regulatory Activities
NE	Non-evaluable
OS	Overall Survival
PD	Progressive Disease
PFS	Progression Free Survival
PR	Partial Response
PT	Preferred Term
RECIST	Response Evaluation Criteria in Solid Tumors
SAE	Serious Adverse Event
SAF	Safety Population
SAP	Statistical Analysis Plan
SAS	Statistical Analysis Software

Statistical Analysis Plan Version draft

Protocol JTX-2011-R01

SOC System Organ Class

SD Stable Disease

TEAE treatment-emergent adverse events

## TRADEMARK INFORMATION

SAS SAS (Statistical Analysis Software) is a registered trademark of SAS Institute Inc.

## 1. INTRODUCTION

This document describes the details of statistical analysis methodology for protocol JTX-2011-R01 (2.0, 03 August 2021), An Open-label, Multi-center, Rollover Study in Subjects with Advanced Solid Tumor Malignancies After Participation in a Vopratelimab (JTX-2011) Clinical Study. As background information, an overview of the study design is provided. Details of the summary and listings to be done are outlined in this document. Note: in this document any text taken directly from the protocol is *italicised*.

## 2. STUDY OBJECTIVES

### 2.1 PRIMARY OBJECTIVE

*The primary objective is to evaluate the long-term safety of continued treatment with vopratelimab monotherapy or combination treatment.*

### 2.2 SECONDARY OBJECTIVES

*The secondary objective is to evaluate the progression free survival (PFS) in subjects treated with vopratelimab monotherapy or combination therapy.*

### 2.3 EXPLORATORY OBJECTIVES

*The exploratory objectives are as follows:*

- *Examine changes from baseline in parent protocol in pharmacodynamic biomarkers including but not limited to phenotypes of immune cell subsets after treatment with vopratelimab monotherapy or vopratelimab in combination with nivolumab or in sequence with ipilimumab.*
- *Examine the correlation between pharmacodynamic biomarkers and duration of response and PFS.*

## 3. STUDY ENDPOINTS

### 3.1 PRIMARY ENDPOINT

- Incidence and severity of treatment-emergent adverse events (TEAEs), serious TEAEs, and discontinuation due to adverse events (AEs) evaluated using National Cancer Institute (NCI) Common Technology Criteria for Adverse Events (CTCAE) version 5.0 and death

### 3.2 SECONDARY ENDPOINTS

- Progression free survival (PFS), duration of response (DOR) as per RECIST version 1.1 and overall survival (OS)

### 3.3 EXPLORATORY ENDPOINTS

- Changes from baseline in parent protocol in pharmacodynamic biomarkers including but not limited to phenotypes of immune cell subsets after treatment with

## Statistical Analysis Plan Version draft

Protocol JTX-2011-R01

vopratelimab monotherapy or vopratelimab in combination with nivolumab or in sequence with ipilimumab.

## 4. STUDY DESIGN

*This is a rollover study that is designed to provide continued access to vopratelimab for eligible subjects with advanced solid tumor malignancies who have previously participated in a vopratelimab study (the parent study) after closure of the parent study.*

*Eligible subjects must have tolerated vopratelimab in the parent study without significant toxicities that otherwise would preclude further dosing in the opinion of the Investigator and/or Sponsor. Subjects must also be expected to receive continued benefit from treatment with vopratelimab in the opinion of the Investigator and/or Sponsor.*

*Subjects will continue to receive vopratelimab at the same dose and schedule received in the parent study, and ideally will experience no treatment interruption between the end of participation in the parent study and entry into the rollover study. Any changes to the dose and schedule of vopratelimab must be in accordance with a dose and schedule previously shown to be safe and well tolerated and must be discussed with the medical monitor.*

*Subjects who received combination treatment on the parent study will also continue to receive the partner drug (e.g., nivolumab or ipilimumab) at the same dose and schedule as in the parent study. Any changes to the dose and schedule of nivolumab or ipilimumab must be discussed with the medical monitor.*

*Safety will be evaluated continuously for the duration of a subject's participation. Imaging for disease status will be performed in accordance with institutional standard of care guidelines and must be performed at least every 6 months ( $\pm$  3 weeks).*

*All subjects must sign a new informed consent form to be enrolled in the rollover study. Subjects may continue to receive study treatment until loss of clinical benefit or unacceptable toxicity as defined by the Investigator and/or Sponsor, withdrawal of consent, loss to follow-up, or death.*

### 4.1 TREATMENT ASSIGNMENT AND BLINDING

#### Treatment Assignment

There is no new treatment assignment in the rollover study. Patients in rollover study will continue to receive vopratelimab and any partner drugs administered in the parent study (e.g., nivolumab, ipilimumab).

#### Blinding

The study is not blinded.

Statistical Analysis Plan Version draft

Protocol JTX-2011-R01

## 5. SAMPLE SIZE CONSIDERATION

*Not applicable. Patients on study treatment in a Jounce-sponsored clinical study and eligible for rollover may be enrolled. For the study objectives, no prospective sample size determination is required.*

## 6. STATISTICAL METHODS

### 6.1 GENERAL CONSIDERATIONS

Individual subject listings will be presented for data collected for rollover study. Data listings will be sorted by parent study id, subject number and date collected where applicable.

Table summary may be provided as appropriate. Categorical data will be summarized by frequency distribution (number and percentage of subjects falling within each category). Continuous variables will be summarized by descriptive statistics including N, mean, standard deviation, median, and range (minimum and maximum).

Data analyses will be conducted using the SAS® System (SAS Institute, Inc., Cary, NC, USA) Version 9.4 or above.

#### 6.1.1 BASELINE

Baseline for subjects in the rollover study is defined as the baseline in the parent study.

For deriving time-to-event efficacy endpoints (PFS, OS, DOR), starting date from parent study will be used with details as follows:

- PFS/OS will be calculated from date of the first dose study drug from parent study.
- DOR will be calculated from date of first confirmed response from parent study.

### 6.2 ANALYSIS POPULATIONS

Enrolled subjects will include all subjects who have signed the ICF for rollover study.

*The Safety Population (SAF) will include all subjects who have been treated with at least one dose of study drug in the rollover study.*

### 6.3 TREATMENT MISALLOCATIONS

Not applicable.

### 6.4 STUDY SUBJECTS

#### 6.4.1 SUBJECT DISPOSITION AND COMPLETION STATUS

## Statistical Analysis Plan Version draft

## Protocol JTX-2011-R01

Subject disposition summary will be provided for all subjects categorized by parent study. The summary will include subjects treated, disposition of subjects with respect to treatment discontinuation and end of study status for the rollover study including reasons for treatment discontinuation and study exit will be provided. Deaths within 30 days of last dose and death beyond 30 days of last dose will be summarized separately along with primary cause of death.

Subject disposition listing will also be provided.

#### 6.4.2 DEMOGRAPHICS , BASELINE CHARACTERISTICS

Subject listing for demographics and baseline disease characteristics will be provided.

#### 6.4.3 STUDY DRUG EXPOSURE

Individual listing for study drug administration will be provided for vopratelimab and any partner drugs administered in the parent study (e.g., nivolumab, ipilimumab) for each dose administration with information regarding intended dose/actual dose, dose modification (and reason if any).

Duration of exposure (days) in rollover study will be defined for each subject and also separately for each study drug as follows:

Duration on study drug X (days)= last dose date of study drug X in rollover study– first dose date of study drug X in rollover study +1

Duration on treatment (days)=max(last dose date of each study drug in rollover study) – min(first dose date of each study drug in rollover study) +1

In addition, overall duration of exposure (overall duration of each study drug and duration of treatment) will also be calculated similarly as above counting from first dose in parent study.

Number of treatment cycles in rollover study and total number of treatment cycles (including parent study and rollover study) will be derived for each subject.

For each study drug, cumulative dose received in rollover study and total cumulative dose received (including parent study and rollover study) will be calculated for each subject.

Duration of exposure (in rollover study and overall), number of treatment cycles (in rollover study and total), cumulative dose received cycles (in rollover study and total) will be provided in data listings.

#### 6.4.4 CONCOMITANT MEDICATIONS

## Statistical Analysis Plan Version draft

## Protocol JTX-2011-R01

Individual listings will be provided for concomitant medications. Concomitant medications will be coded by WHO Drug Dictionary. Concomitant medications will include all concomitant medications taken on or after the date of first dose of study drug or any concomitant medication started prior to first dose of study drug that continued beyond the date of first dose of study drug in rollover study.

#### 6.4.5 MEDICAL HISTORY

Medical history will be coded according to the Medical Dictionary for Regulatory Activities (MedDRA) dictionary v23.0 or higher and will be listed.

### 6.5 EFFICACY ANALYSES

The efficacy endpoints include progression-free survival (PFS), duration of response (DOR) and overall survival (OS), all relative to C1D1 of the parent study.

#### 6.5.1 PROGRESSION-FREE SURVIVAL

Progression-free survival (PFS) is defined as the time from the first dose of study drug from parent study until the first documentation of a disease progression or death due to any cause, whichever occurs first regardless of whether the subject receives subsequent anticancer therapy prior to progression. Patients who have no documented progression and are still alive at the time of analysis will be censored at the time of the latest date of assessment from their last evaluable RECIST 1.1 assessment. PFS is defined in months as follows:

$$\text{PFS (months)} = (\text{Date of PD/death or censoring} - \text{Date of the first dose study drug from parent study} + 1) / (365.25/12)$$

Individual subject listing will be provided for PFS including PFS time, event/censor date and event/censoring description.

#### 6.5.2 DURATION OF RESPONSE

Duration of response (DOR) is defined as the time from the first documentation of a subsequently confirmed objective response from parent study until the first documentation of disease progression or death due to any cause, whichever occurs first regardless of whether the subject receives subsequent anticancer therapy prior to progression. For subjects who are alive and progression-free at the time of data cut-off for analysis, DOR will be censored at the last tumor assessment date. Only subjects who have achieved objective response (confirmed CR or confirmed PR) will be evaluated for DOR. DOR is defined in months as follows:

## Statistical Analysis Plan Version draft

Protocol JTX-2011-R01

DOR (months) = (Date of PD/death or censoring – Date of first confirmed response from parent study + 1) / (365.25/12),

The date of PD/death or censoring is the same as defined for PFS.

Individual subject listing will be provided including DOR, BOR, start date of response, event/censoring date and event/censoring description. Start date of subsequent anticancer therapy will be also be included when applicable.

### 6.5.3 OVERALL SURVIVAL

Overall survival (OS) is defined as the time from the first dose of study product from parent study until death due to any cause. For patients who are alive at the time of analysis, OS will be censored on the last date when patients are known to be alive.

OS is defined in months as follows:

OS (months) = (Date of death or censoring – Date of the first dose of study drug from parent study + 1) / (365.25/12).

Individual subject listing will be provided.

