4.2 Secondary Objectives

Evaluate the progression free survival (PFS) in subjects treated with vopratelimab monotherapy or combination therapy

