9 OVERALL STUDY ASSESSMENTS

Duration of participation on this study will be dependent on the amount of time a subject derives clinical benefit. An End-of-study visit will be performed 28 days (\pm 7 days) after the last dose of study treatment.

9.1 Rollover Entry/Cycle 1 Day 1

Enrollment into the rollover study should occur upon exit from the parent study to avoid any interruptions in study treatment administration.

All assessments should be performed prior to vopratelimab dosing, unless otherwise noted.

- Signing of informed consent form.
- Review eligibility criteria to determine whether a subject may enter the rollover study.
- Physical examination.
- Vital signs pre-and post-infusion.
- Weight.
- Serum or urine pregnancy test for women of childbearing potential. The pregnancy test will not be required for women who are surgically sterile or who are greater than 1 year post-menopausal.
- Laboratory assessments including hematology and chemistry; additional laboratory measurements may be performed in accordance with institutional guidelines.
- Pharmacodynamic biomarkers; Collection of samples may be discontinued at any time per the Sponsor's discretion.
- Record ongoing concomitant medications and AEs.
- Study treatment (vopratelimab \pm partner drug) administration on the same dose and schedule as a subject was receiving at the time of discontinuation from the parent study. Study drug administration between the parent and rollover study should be maintained per the dose and schedule on the parent study. Any changes to the dose and schedule of vopratelimab must be in accordance with a dose and schedule previously shown to be safe and well tolerated and must be discussed with the medical monitor. Any changes to the dose and schedule of nivolumab or ipilimumab must be discussed with the medical monitor.

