11 STATISTICAL ANALYSES

11.1 Endpoints

Safety and efficacy endpoints, including exposure to the investigational study drug, incidence and severity of treatment-emergent serious and non-serious AEs, investigational study drug discontinuation reason, and death, will be derived.

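### Must the SAP be changed because deaths after the End-of-study visit feed the late-death summary and the OS listing but are not systematically collected?

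*SAP*

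**What the plan says.** **SAP.** The primary endpoint in 3.1 ends with "Common Technology Criteria for Adverse Events (CTCAE) version 5.0 and death". Section 3.2 adds OS to PFS and duration of response as secondary endpoints. Section 6.5.3 defines OS from the first dose in the parent study to death from any cause. For patients alive at the analysis, "OS will be censored on the last date when patients are known to be alive". The only OS output is a listing by subject. Section 6.4.1 plans a disposition summary in which "Deaths within 30 days of last dose and death beyond 30 days of last dose will be summarized separately along with primary cause of death".

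**Protocol.** The single secondary objective (4.2) is "Evaluate the progression free survival (PFS) in subjects treated with vopratelimab monotherapy or combination therapy". OS is not an objective, but 11.1 covers safety and efficacy endpoints and says that "investigational study drug discontinuation reason, and death, will be derived". On timing, section 9 states: "An End-of-study visit will be performed 28 days" (± 7 days) after the last dose. That visit is the last column of both schedules of events.

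AEs are recorded up to that visit (10.8.2). SAEs are recorded until they resolve or new therapy starts, or for 28 days after the final dose if there is no new therapy (10.9.5). After that, an SAE with a possible link to study drug must still be reported if the investigator discovers it. Neither document has a survival follow-up visit, a vital-status call or a records check.

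**The concern.** The SAP appears to promise more than the protocol collects. All-cause OS and a count of late deaths with cause suggest complete knowledge of vital status, yet scheduled contact stops at about the point where the late-death category begins. Deaths linked to open or related events have a reporting route. A new, unrelated death two months after the last dose has none that is written down. The late-death row could then be too low and its causes unrepresentative, in a study whose primary objective is long-term safety. Known-alive dates for subjects off treatment would also cluster near the End-of-study visit. Most subjects stop for loss of benefit or toxicity, so that censoring would probably be informative if anyone later drew a survival curve. The SAP mentions none of this.

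**Working it through.** The plan gives no sample size, event count or survival assumption, so there is no figure of its own to reproduce. The check sets the time windows against the 30-day split, sizes the gap under a stated assumption, and asks which planned output depends on it.

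**1. Windows for a subject who has stopped treatment** (Protocol 9, 10.9.5; SAP 6.4.1)
- Earliest visit: 28 − 7 = day 21, which is 30 − 21 = 9 days before the split.
- Target visit: day 28, which is 2 days before the split.
- Latest visit: 28 + 7 = day 35, which covers days 31 to 35 of the late category.

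**2. Subjects still on treatment.** Day 35 is not an outer limit for them. On the six-weekly schedule (Protocol Appendix 1) the next visit falls at 42 ± 3, so days 39 to 45. Protocol 7.1.1 provides for delays of more than 14 days, and Table 1 for holds that can reach 6 weeks. A subject who dies on day 40 while waiting for the next dose belongs in the late row and is still under observation.

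**3. Routes for other late deaths.** Ongoing AEs are followed to the final visit or satisfactory resolution (10.8.2). SAEs are covered until resolution or new therapy, and possibly related SAEs are reported if discovered (10.9.5). Inside the window, deaths from cancer are captured too: symptoms of progression are reported as AEs (10.8.1), an event that results in death is an SAE (10.9.1), and the fatal event must be recorded (10.8.5). The limit is therefore one of time, not of the rule on disease progression.

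**4. Size, under an assumption.** Take exponential survival after the last dose with median *m* months, and 365.25/12 = 30.4375 days per month. The share of deaths beyond day 30 that fall after day *d* is

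S(d)/S(30) = exp(−ln 2 × (d − 30) / (30.4375 m)).

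| Median *m* (months) | after day 35 (5 days past the split) | after day 45 (15 days past the split) |
|---|---|---|
| 3 | 96.3% | 89.2% |
| 6 | 98.1% | 94.5% |
| 12 | 99.1% | 97.2% |

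Let *s* be the share after day 35 and *c* the fraction of those deaths that still reach the database. The row then holds (1 − s) + c·s of the true late deaths:
- c = 0: 3.7%, 1.9%, 0.9% for *m* = 3, 6, 12.
- c = 0.5: 51.9%, 50.9%, 50.5%.

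Completeness is thus close to *c* itself, and the documents do not give *c*. Nor can a tilt in cause be sized. That would need separate capture rates for related and unrelated deaths, and even related late deaths count only if discovered.

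**5. What depends on it**
- OS: a listing by subject. No Kaplan-Meier estimate or test is planned.
- Late-death row: a descriptive count of the deaths in the database.
- Primary endpoint: incidence and severity of treatment-emergent events, and death, all summarised descriptively. There is no sample size calculation and no interim analysis.

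A caveat would leave each listed date and each count as it is.

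**The case for a change.** The best case for a change is that it costs a sentence. A SAP should not call something OS, or tabulate late deaths by cause, without saying that the protocol does not follow survival. The death table is a planned safety summary, and a reader outside the study could take the row as complete. The censoring rule in 6.5.3 also covers only patients alive at the analysis, while many subjects off study will have unknown status.

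Much of this stands. The mismatch is real, and the row may be selective by cause. Three things limit it:
- The eCRF is not among the documents. The SAP expects a cause for late deaths (6.4.1) and a start date for subsequent anticancer therapy (6.5.2), which suggests some post-treatment fields. Whether these are filled systematically cannot be determined.
- The gap on unknown vital status has an obvious filling: censor at the last date known alive, as the rule already does for the others. An analyst would do this without instruction.
- Removing OS would discard a harmless listing. Promising that no OS estimate will be derived adds nothing, since none is planned. Adding survival follow-up would be a protocol change out of proportion to a descriptive rollover study meant to give continued access.

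**Conclusion.** The observation is correct, but it calls for no change. After treatment ends, late deaths are not systematically collected. If survival after the last dose is exponential with a median of 3 to 12 months, 96% to 99% of deaths beyond day 30 come after the latest permitted End-of-study visit. How many of those still reach the database, and whether their causes are representative, cannot be known from the documents.

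The consequence is small because nothing inferential rests on these outputs. OS is listed, the late-death row is counted, and censoring at last known alive is conventional. A relabelled row would show the same number. The limit is evident to anyone who reads the schedule of events beside the table. Whoever produces the outputs can reasonably footnote the row and the listing as reported deaths, which needs no revision of the SAP. The conclusion would differ if a survival curve, or a comparison of late mortality, were planned.
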